18.8 Guidelines for Emergency Unblinding of Coded Intervention

a. The following events MAY require emergency unblinding of Coded Intervention:

- A compelling medical need as determined by a physician, e.g., occurrence of a severe or life-threatening reaction, inclusive of an adverse drug reaction, which may have been attributable to Coded Intervention, or existence of a condition where the knowledge of the patient's treatment assignment would directly influence or affect his/her immediate care;
- ingestion of the Coded Drug by persons other than the patient or in excessive quantity;
- exposure of a pregnant woman to the Coded Intervention;
- exposure of a child to the Coded Intervention;

Note: Adverse drug reactions should be reported as required per [Section 16.0](#) of this protocol.

b. Procedure for Emergency Unblinding

The procedure for unblinding the treatment assignment for a patient is as follows:

- All unblinding must be done by the registering physician or designee.
- Call the Washington Poison Control (WPC) collect at [name] or at [name] if calling from within Washington State. The WPC is accessible 24 hours per day, 365 days per year for unblinding calls. Informational calls should be directed to the Data Operations Center in Seattle during standard business hours.
- Provide the WPC with the following information:

Study number: **S1600**

SWOG patient number

Patient name

Coded Intervention ID number and bottle number

Name and telephone number of the caller

Reason unblinding is required

- Unblinding for ingestion of the Coded Intervention by a pregnant woman will not require the authorization of a resource physician. (The resource physicians for this study are listed at the end of this section.)
- Unblinding for ingestion of the Coded Intervention by a child will not require the authorization of a resource physician.
- Unblinding for ingestion of the drug either in excessive amounts or by a person other than the patient will be done ONLY when a compelling medical need exists and/or unblinding has been authorized by a resource physician.
- Unblinding for a "compelling medical need" must be authorized by a physician designated as a resource physician for this protocol.

18.9 Translational Medicine Study Stool Microbiome

The stool microbiome of patients in a randomized control trial of perioperative immunonutrition for reduction of complications following radical cystectomy and urinary diversion.

a. Objectives:

1. To describe the microbiome of the gut in patients undergoing radical cystectomy and urinary diversion prior to initiation of immunonutrition or a nutrition control.
2. To define the microbiome change in patients undergoing radical cystectomy and urinary diversion after they have received blinded immunonutrition or control nutritional supplement.
3. To correlate cancer treatments, postoperative complications, specifically infections, and nutritional status with microbiome composition

b. Background

Radical cystectomy is associated with significant complication rates; most studies find 60% complication rates across the world and 30% readmission rates. The **S1600** clinical trial is examining a novel immunonutritional intervention with the goal of reducing these post-operative complications.

Microbiomes are made up of microbiota that live in and on humans; microbiomes exist in the urinary tract, skin, gut/GI tract and other systems of the body. A great deal of research has been done with the microbiome in patients undergoing colorectal and pancreatic surgery. (1,2) The microbiome for both of these surgeries has been found to be associated with perioperative outcomes and complications. (3,4) Complications and infections specifically are associated with microbiome in the perioperative period. (5,6) A serious complication of surgery can be an intestinal anastomotic leak, which is potentially driven by the microbiome. (7,8) There is data in humans that the gut microbiota have a role in recovery from surgery involving the gastrointestinal tract, specifically anastomotic leak and infections. (9) Testing of probiotics has demonstrated that the complex mucosal immune system can be modified with probiotics in colorectal cancer and can improve the hosts' immune responses. (10) In addition, modifications of the microbiota have been used to optimize therapeutic interventions in mice receiving immunotherapy. (11) In addition, a recent meta-analysis of patients undergoing gastrointestinal surgery benefited from probiotics and synbiotics, and they were associated with lower infectious complications. (12,13,14,15) Therefore, microbiome profiling may enable tailored interventions specific to each patient to prevent postoperative complications. The microbiome may also be modified by the nutrition, specifically immunonutrition, synbiotics or probiotics. (16)

There is a critical gap in knowledge about which radical cystectomy patients are most likely to experience postoperative complications and how best to prevent them. Importantly, there are no consistent predictors of which patients will develop postoperative complications. Given the high rate of complications and the frequent occurrence of this operation, there is enormous room for improvement in the perioperative care for these patients, and identification of an intervention to reduce complications could have a large impact. In this proposal we will examine

associations between the gut microbiome and postoperative complications, in an attempt to identify a potentially modifiable predictor of complications. In addition, we will investigate the impact of the immunonutrition intervention on the gut microbiome in patients undergoing radical cystectomy.

Preliminary studies

Key publications include details on how the microbiome drives key portions of disease and can be modulated with novel therapies. In particular, using 16sRNA sequencing has been established as an association between the gut microbiome and immune modulated diseases in cancer patients, which has led to the identification of novel microbiome-targeted therapeutics. (17)

An additional key publication describes the diversity of the gut microbiome and how the host factors of the microbiome vary between different hosts (different humans with varying diseases) and over time. The presence of more diverse intestinal microbiomes has been correlated with anti-inflammatory properties. (18) This provides insight that the microbiome can be modified by increasing diversification of the microbiome with factors such as nutrition. Importantly the microbial community can be targeted with clinical treatments. (19) For example, one large study found a difference in *C. difficile* infection rates among patients with and without immunonutrition, indicating that there may be advantages to modulating the gut with immunonutrition. (20)

c. Endpoint(s) to be used in analyses:

1. Post Operative complications (any vs. none)
2. Post Operative infections (yes/no)
3. Nutritional status (malnourished vs. adequate nutrition)
4. Other cancer treatments (preoperative chemotherapy vs no preoperative chemotherapy)

d. Experimental approach, validated assays employed and expertise:

This translational study to examine changes in the gut microbiome with intervention is being incorporated into the currently activated and enrolling SWOG **S1600** trial. Patients' stool samples will be collected with the Omniprene-GUT kit. This kit allows the patient to collect and preserve the samples from the comfort of their own home. Patients will be asked to collect a stool specimen and place a small sample on the kit spatula. This is then placed into the tube provided. With the Omniprene-GUT kit the yield of DNA is not influenced by temperature, thus it should be able to be shipped at any time of the year in any climate. (21) Once the samples have been collected they are stable in the test tube for 60 days at room temperature. Collection timepoints and instructions are located in [Section 15.2](#). They will begin their nutritional supplements 5 days before surgery and then undergo surgery per the **S1600** protocol. As the **S1600** protocol dictates strict timing of drink delivery, the first specimen can be collected anytime after **S1600** enrollment, but before initiation of their first nutritional drink (control or immunonutrition). After discharge from the hospital, we will have them collect the first bowel movement that occurs at home (+/- 2 days). Although waiting until after discharge means the timing of collection of the post-surgical sample will vary based on each patient's duration of hospitalization, collection of the sample during hospitalization at each participating institution is anticipated to be logistically

difficult and therefore unreliable. These kits have been used in [name] lab previously for other studies that require shipping the specimens internationally, and extraction of these shipped samples has yielded the same results as fresh samples collected locally in the lab. (22) SWOG Biospecimen Bank will process specimens per the Omniprene-GUT website. The samples will be stored in -80 degree freezer until end of study. Frozen samples will be shipped from SWOG Biospecimen Bank to the University of Colorado for analysis. DNA will be extracted and sequenced using standard 16s rRNA technique, using the DNeasy PowerSoil kit from Qiagen using the manufacturer's instructions, with the addition of a 65 degree incubation step and homogenization with bead-beating rather than vortex. (23) The bead-beating will facilitate release of DNA from gram positive bacteria.

Bioinformatic analysis of the 16s rRNA amplicon sequences will be conducted as follows: The reads will be processed using QIIME v1.9.1. After filtering out reads containing Phred scores <30 or chimeric sequences detected by USEARCH v6.1, then clustered forward reads will be used for *de novo* operational taxonomic units at a 97% similarity threshold using UCLUSTref v1.2.22q and greengenes v13_8. After that, the operational taxonomic units are translated to taxa (for example, genus and species) using RDP v2.2. A phylogenetic tree of operational taxonomic units with FastTree v2.1.3 will be used to evaluate bacterial diversity (phylogenetic diversity index, sums total phylogenetic branch length observed in a subject) (unweighted and weighted UniFrac distances quantify unique versus shared phylogenetic tree branch length between two samples). Rarefaction will be used to accommodate differential library sizes. This bioinformatics analysis is standard operating procedure for [name] lab and is available freely reproduced using Qiita (qiita.ucsd.edu/study/description/10564). (24) The bioinformatics processing pipelines for microbiome data continue to evolve with best-practices and the state-of-the-art constantly improving. Accordingly, alternative processing pipelines may be considered at the time of analysis.

Once all the samples have been sequenced, bioinformatics analysis (described above) will be conducted at the University of Colorado by analysts experienced in the bioinformatics analysis of stool microbiome. (25) Statistical analyses and correlations with endpoints (described in Section 18.9.e) will be conducted at the SWOG Statistics and Data Management Center.

e. Statistical Plan:

Aim 1: The objective of Aim 1 is to describe the baseline microbiota. Alpha-diversity metrics for each patient's baseline samples will be calculated from rarefied data. Beta-diversity metrics including UniFrac distance, Bray-Curtis dissimilarity, and Aitchison distance will be calculated from rarefied data and ordination plots will be generated. For individual taxon level data, rank abundance plots will be generated and prevalence of particular bacterial taxa will be estimated. Clustering, based on beta-diversity, will be used to examine possible enterotypes.

Aim 2: The objective of Aim 2 is to assess change in the microbiota between baseline, after nutrition drinks and surgery (post-operative). We will first assess the change using all patients (across both arms). To assess the change in alpha-diversity, the difference in Shannon Index between predrink, pre- and post-operative profiles will be calculated for each individual and compared using a paired t-test at the nominal $\alpha=0.05$ level. Similarly, beta diversity distance matrices will be calculated using the pooled (baseline and post operative) samples to generate a $2n \times 2n$ matrix which will be compared using PERMANOVA with patient

as a stratification variable; 9,999 permutations will be used to generate a p-value with significance called at the $\alpha=0.05$ level.

For individual taxon level analyses (quantified at the genus level), taxa present in less than 15% of samples or with average relative abundance <0.1% will be filtered. Sparsity will be reduced by adding a pseudocount to raw counts or by application of Bayesian-multiplicative replacement. De-sparsified relative abundance data will be center-log-ratios transformed to accommodate compositionality concerns and encourage normality. Subsequently, the change between post- and pre-operative (transformed) data will be calculated for each taxon (on each patient) and the change will be compared using a paired t-test. Benjamini-Hochberg false discovery rate (FDR) will be controlled at the 10% level.

We will repeat the analyses within each arm, separately. Comparisons (in change) across arms will be conducted in Aim 3 (below).

Aim 3: The objective of Aim 3 is to assess the association between microbiome profiles and dichotomous clinical outcomes, including preoperative chemotherapy, post-operative complications, post-operative infections, and post-operative nutritional status. Each outcome will be analyzed separately.

For the primary outcome of post-operative complications, we will assess whether (1) baseline microbiome profiles (2) post-operative microbiome profiles and (3) change in microbiome profiles are associated with post-operative complications.

For the baseline analyses (1) and post-operative analyses (2), we will first restrict attention to patients randomized to the specialized immune-modulating nutrition drink arm. Then we will assess the association between alpha diversity (Shannon index) and complications by regressing alpha diversity on indicator for complications and additional covariates. A 1-df test will be used to evaluate the association with complications at the nominal $\alpha=0.05$ level. Beta-diversity analysis will proceed by calculating UniFrac, Bray-Curtis, and Aitchison metrics which will be compared between patients with and without complications using a logistic version of the microbiome regression-based kernel association test (MiRKAT), a generalization of PERMANOVA with improved covariate adjustment, calling significance at the $\alpha=0.05$ level. Finally, transformed taxon abundances (as in Aim 2) will be compared between patients with/without complications by regressing taxon abundance on an indicator for complications, again adjusting for additional covariates. A 1-df test will again be used with FDR controlled at the 10% level.

For baseline and post-operative microbiome samples, we will then repeat these analyses restricting analyses to patients in the control arm and also pooling across arms (with adjustment for arm). Finally, within the pooled analyses, we will further assess whether the microbiome modifies the association between treatment and outcomes. For alpha diversity and individual taxon analyses, we will include two-way interactions between Shannon index or individual taxon abundances, respectively, in the corresponding models and again evaluate significance using a 1-df with FDR controlled at 10%. For beta-diversity analysis, we will embed the distance matrices into kernel metrics (as in MiRKAT), but then we will use a logistic kernel-machine interaction test to assess whether associations between outcome and treatment are heterogeneous by microbiome beta-diversity profiles.

To examine whether change in microbiome profiles is related to preoperative chemotherapy, will conduct similar analyses as in the baseline and post-operative samples, except for alpha diversity and individual taxa, we will, respectively, use change in Shannon Index and change in taxon abundance. For beta-diversity analysis, we will calculate paired analogues of the UniFrac, Bray-Curtis, and Aitchison distances developed by SWOG.

Following analysis of the primary endpoint, we will repeat the analysis using post-operative complication and infection status and post-operative nutritional status as endpoints instead.

For all analyses, robust and non-parametric alternatives, as well as other data transformations, will be used if statistical assumptions are violated. If necessary, analyses will be adjusted for additional covariates, possibly including: age, BMI, underlying disease (renal disease/etc), sex, baseline nutritional status, preoperative chemotherapy, muscle mass, etc. If necessary, we will also adjust for technical covariates such as storage time and time from surgery to collection (of the post-operative sample). Possible batch effects will be assessed and removed if present per SWOG TM guidelines: the SWOG statistical center has previously validated the use of ComBat (on CLR transformed data) for mitigating batch effects in 16S data.

Sample Size and Power Considerations:

For Aim 1, with a sample size of 73 patients per arm (146 patients, total), we will be able to estimate the prevalence of particular enterotypes or particular bacterial taxa to within 8.1% (95% confidence interval) using all baseline samples.

For Aim 2, we anticipate 80% power to detect a change in alpha-diversity from baseline to post-surgery of 0.23 and 0.33 standard deviations (sds) using all patients and patients in a particular arm, respectively. For individual taxa, conservatively assuming that 90% of taxa do not have change from baseline to post-surgery, then at the FDR=10% level, we anticipate 80% average power to identify a taxon with change in abundance of 0.29 and 0.41 sds, using all patients and patients in an individual arm, respectively.

For Aim 3, we calculate minimal detectable effect sizes assuming 42%, 65%, and 53% complication rates in the experimental arm, control arms, and overall, respectively. Then for the baseline and post-operative microbiome analyses, we anticipate 80% power to detect a difference in alpha diversity between patients with/without complications of 0.67, 0.69, and 0.46 sds, in the experimental arm, control arm, and pooled across arms, respectively. For individual taxon analyses, again assuming that 90% of taxa are not differentially abundant between, then we anticipate 80% average power to identify a taxon with difference in abundance between patients with/without complications of 0.83, 0.86, and 0.58 sds, in the experimental arm, control arm, and pooled across arms, respectively. Minimal detectable effect sizes for analyses examining change are analogous except based on differences in alpha diversity and taxon abundance.

- f. Data analysis performed by:
The CU bioinformatics department (informatics and quantification) and SWOG statistical center (correlative analyses)
- g. Laboratory
[name].-
University of Colorado
[name]
[name]
Email: [contact]
[contact]

References

- 7 Gershuni VM, Friedman ES: The Microbiome-Host Interaction as a Potential Driver of Anastomotic Leak. *Curr Gastroenterol Rep* 21:4, 2019.

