10.2 Secondary Endpoints

a. In addition to grading, complications will be defined using surgery-specific categories (ileus, deep vein thrombosis, pneumonia, wound infection, urinary tract infection, return to operation room, pulmonary embolus, myocardial infarction, cerebral vascular accident, dehiscence, sepsis, respiratory failure, bowel leak, urine leak, small bowel obstruction, death, or other). Post-operative ileus will be defined as a delay in feeding of greater than or equal to five days post-operatively.

b. **Postoperative Infections.** Infectious complications are defined by the use of non-prophylactic antibiotics to treat infection. In addition, infections will be categorized by intra-abdominal infection or surgical site infection.

- c. **Anthropometrics & Body composition.** Changes in fat mass and non-bone lean tissue (muscle mass) will be assessed by dual-energy X-ray Absorptiometry (GE Lunar DXA, Software version 13.5 or newer version, Madison, WI, or Hologic, Software version APEX 5.5.3.1 or newer version) at baseline and 30 days. The fat-free mass index (FFMI) and the appendicular skeletal muscle will be examined over time. Body weight (in a hospital gown without shoes) will be measured using a digital scale accurate to ± 0.1 kg. Height will be determined using a wall-mounted stadiometer (± 0.1 cm). See [Appendix 18.3](#) for further information.
- d. **Quality of Life.** Functional Assessment of Anorexia/Cachexia Therapy (FAACT) will be completed by the patient at baseline and 30 days post-operation. (119) The FAACT trial outcome index and anorexia subscales were used in our pilot and the SIM showed better scores than the ONS group but the differences were not statistically significant ($P=0.15$ for both), but the pilot was underpowered for this outcome. Also, the anorexia and cachexia subscale asks about issues common after RC such as: taste alterations, appetite, early satiety, and pain while eating. These data are crucial for optimizing nutrition interventions to help patients.
- e. **Readmission Rates.** Readmission will be defined as admission to any hospital after discharge home until 90 days after surgery. The reason for readmission will be recorded.

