15.2 Specimens for the TM Stool Microbiome (**REQUIRED IF PATIENT CONSENTS**)

The fecal microbiome of patients in a randomized controlled trial of perioperative immunonutrition for reduction of complications following radical cystectomy and urinary diversion.

Stool specimens for translational medicine and banking (submitted to the SWOG Biospecimen Bank – Solid Tissue, Myeloma and Lymphoma Division, Lab #201) are considered optional for the participant.

- a. With patient's consent specimens must be submitted at the time points listed below.
 1. After registration, but before beginning nutritional drink
 2. After nutrition/before surgery (at least 4 days (+/- one drink) of drinks completed)

3. First bowel movement on return to home (+/- 2 days).
- b. Omnipgene-GUT Kit Stool Ordering

Immediately after identifying a patient for the trial, sites must contact SWOG Biospecimen Bank to order Omnipgene-GUT kits via the following URL: <https://kits.bpc-apps.nchri.org>. Orders placed by noon Eastern should be received within 3-4 business days.
- c. Omnipgene-GUT Kit Stool Labeling

Sites will be instructed to label tubes with:

 - SWOG patient number
 - Patient initials
 - Specimen type
 - Collection date

NOTE: The collection date will be filled by the patient on the tube and the Intake Calendar. Sites must verify the date has been added on the tube prior to shipping.
- d. Specimen Collection and Submission Instructions

Collection kits will be sent home with the patients at 2 different times to reduce patient error.

 - (1) 2 kits will be provided after registration for the collection of:
 - After registration, but before beginning nutritional drink
 - After nutrition/before surgery (at least 4 days of drinks completed)
 - (2) 1 kit will be provided after surgery when site staff provides nutritional drinks

Due to the sensitive nature of the collections, patients will collect the specimens at home. Patients must be instructed to bring their specimen back to the site on a subsequent visit.

Site phone calls

- Call the patient at home six days before the surgery date to remind patients to collect their stool sample.
- Call patient prior to 30-day follow-up to bring their samples to appointment.

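### Aim 3 of the stool sub-study tests a post-discharge sample against complications and infections that may precede it, and does not name the post-drink, pre-surgery sample as a profile

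*Combined protocol and SAP*

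**What the plan says.** Section 15.2a sets three stool time points. The first is "After registration, but before beginning nutritional drink". The second is "After nutrition/before surgery (at least 4 days (+/- one drink) of drinks completed"). The third follows discharge; Section 18.9d puts it as "we will have them collect the first bowel movement that occurs at home (+/- 2 days"). Section 18.9d accepts that "the timing of collection of the post-surgical sample will vary based on each patient's duration of hospitalization", and explains that collection in hospital would be unreliable.

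For complications, Aim 3 in Section 18.9e asks whether "1) baseline microbiome profiles (2) post-operative microbiome profiles and (3) change in microbiome profiles are associated with post-operative complications". It then repeats the work for infection and post-operative nutritional status. Within the pooled baseline and post-operative analyses it also tests whether the microbiome modifies the treatment effect. Section 10.2b states: "Infectious complications are defined by the use of non-prophylactic antibiotics to treat infection". The background in Section 18.9b describes the work as "in an attempt to identify a potentially modifiable predictor of complications".

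The only timing adjustment is for time from surgery to collection, and only if judged necessary. Antibiotic exposure is not among the covariates named.

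**The concern.** A complication during the index stay happens before the third sample. For an in-hospital infection the difficulty is sharper, because the outcome is itself defined by antibiotic treatment given before that stool is collected. A difference between patients with and without the event may then show what the event or its treatment did to the gut flora. The same holds for any change score that ends at the third sample. It also holds for an interaction in which the supposed effect modifier is measured after the outcome.

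At stake is the reading of Aim 3. A consequence of infection could be reported as a modifiable predictor. Meanwhile the one sample that both precedes every post-operative outcome and reflects the drinks is not listed as a profile to be tested.

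**Working it through.** **Order of samples and events**

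- Sample 1 (before drinks): precedes every complication, does not reflect the drinks, and is Aim 3 profile (1).
- Sample 2 (after drinks, before surgery): precedes every complication, reflects the drinks, and is not named as an Aim 3 profile.
- Sample 3 (after discharge): follows in-hospital events, precedes later ones, and is Aim 3 profile (2).
- Change is Aim 3 item (3), but the pair is not stated. In Aim 2, Shannon change refers to all three profiles, taxon change compares post- with pre-operative data, the beta-diversity matrix pools baseline and post-operative samples, and the power text refers to baseline to post-surgery.

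**The plan's detectable effects**

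Inputs from Section 18.9e: 73 per arm (146 in total), complication rates of 42%, 65% and 53%, 80% power, alpha 0.05. For a comparison of means between patients with and without a complication:

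MDE = (1.960 + 0.842) × sqrt(1/(n·p) + 1/(n·(1−p)))

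- Experimental arm: groups of 30.7 and 42.3, MDE 0.66 (stated 0.67).
- Control arm: groups of 47.5 and 25.5, MDE 0.69 (stated 0.69).
- Pooled: groups of 77.4 and 68.6, MDE 0.46 (stated 0.46).

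The stated figures reproduce with a two-sided test. A one-sided test gives 0.59, 0.61 and 0.41 and does not fit.

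**Comparator for infection**

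The pooled 0.46 SD belongs to a 53% split. Taking the 25% infection rate cited in Section 2.0 (a literature rate, not a design assumption), the groups are 146 × 0.25 = 36.5 and 109.5:

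MDE = 2.80 × sqrt(1/36.5 + 1/109.5) = 2.80 × 0.191 = 0.54 SD

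**Possible size of the artefact (assumptions, not document figures)**

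Let f be the share of infections treated before sample 3, and s the resulting fall in the Shannon index, taken as 0.5 to 1.0 SD. With no causal effect of the microbiome, the infection contrast is f × s. The chance of a significant two-sided test is about Φ(f·s/0.191 − 1.96).

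- f = 1: contrast 0.5 to 1.0 SD, chance 74% to above 99%.
- f = 0.5: contrast 0.25 to 0.5 SD, chance 26% to 74%.

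For any complication, if every infection counts as a complication, the shift is diluted by 0.25/0.53 = 0.47. That gives 0.24 to 0.47 SD at f = 1 and 0.12 to 0.24 SD at f = 0.5, against 0.46 SD. Only the top of the first range reaches the detectable effect.

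**Effect of the remedies on power**

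Adding sample 2 as an Aim 3 profile keeps the same n and split, so the MDEs stay at about 0.66, 0.69 and 0.46 SD. Limiting sample 3 to complications that start after it, and excluding patients whose complication came first (share q, assumed), leaves 77.4 × (1 − q) cases against 68.6 without a complication:

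- q = 0.25: 58 cases, pooled MDE 0.50 SD.
- q = 0.50: 39 cases, 0.56 SD.
- q = 0.75: 19 cases, 0.72 SD.
- q = 0.90: 8 cases, 1.06 SD.

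**The case against.** The formal objective is to correlate microbiome composition with treatments, complications and nutritional status, and Aim 3 is framed as association. One of its outcomes, preoperative chemotherapy, precedes every sample. The alpha-diversity and taxon models take the microbiome as the response. Predictor language appears only in the background, the variable collection time is disclosed with its reason, and the sub-study is optional. All of this is fair, and it limits the weight of the point. It does not remove it: the effect-modification test on post-operative samples is more than description, and the plan gives no rule for reading a sample-3 result when the event came first. Adjusting for time from surgery to collection does not restore the order.

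A reader might go further and infer that most complications precede sample 3. Nothing in the documents supports that. The complication window runs to day 30 (Section 11.1), infections are examined at days 30 and 90 (Section 11.2), and Section 18.9b cites 30% readmission, so some events can follow the sample.

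A reader might also infer that the pre-surgery sample is excluded from Aim 3. That too is more than the text says, because the sample may enter through change, given how Aim 2 describes it. Nor does Aim 3 lack a valid predictor: the baseline profile is one, and it has its own planned interaction test.

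**Conclusion.** The point holds as one of specification and interpretation. Aim 3 does not handle the order of event and sample 3, does not name the pre-surgery profile, and leaves the pair for change undefined. No stated figure is wrong, and no primary or secondary conclusion of the trial depends on this sub-study.

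How many patients are affected cannot be derived from the documents. The 0.5 to 1.0 SD infection contrast rests on all infections coming first, on a 25% rate from the literature, and on an assumed antibiotic effect. Its lower end lies just below the 0.54 SD detectable effect. The calculation shows that an artefact large enough to be declared significant is possible, not that one will occur.

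**What to change.** In Section 18.9e:

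- Name the pre-surgery profile and the baseline-to-pre-surgery change as Aim 3 analyses for complications and infections.
- Use the baseline and pre-surgery samples for the predictive and effect-modification analyses.
- State which pair of samples each change analysis uses.
- Report results from the post-operative sample, and from any change ending at it, as descriptive associations that may reflect the complication or its treatment.
- If onset dates are captured, add a sensitivity analysis limited to events that start after the stool collection date.

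The first four items need no new specimens, leave the detectable effect per test unchanged, and add a few exploratory tests. The last may need extra data: stool collection dates are recorded, but the visible text on the day-30 and day-90 assessments (Sections 7.7, 7.8 and 14.4) does not show onset dates. It would also have less power, with a pooled detectable effect of about 0.50 to 1.06 SD if 25% to 90% of complications come first (an assumed range).
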